4.0 Study Endpoints

*4.1 Describe the primary and secondary **study** endpoints. See links below for discussion of study endpoints and how they may differ from study objectives. These are most common in clinical trials but are sometimes applicable to other types of biomedical research, as well as social, behavioral, or educational research. See link below for a discussion.*

https://docs.google.com/document/d/1Wocz7K7a0hCQJPPO_khh511SQjhGDDGHzcOPRHR5Tw/edit?usp=sharing

Delay discounting: Change in discounting rates will be compared within-subjects between pre intervention and post intervention. In addition, differences in discount rates will be compared between groups (EFT and CET).

Alcoholic Drinks: Change in drinks per day and number of positive breath alcohol samples (BrAC) will be compared within-subjects between pre intervention and post intervention. In addition, differences in drinks per day and number of positive BrAC samples will be compared between groups (EFT and CET).

Alcohol Demand: Change in demand for alcohol will be compared within-subjects between pre intervention and post intervention. In addition, differences in alcohol demand will be compared between groups (EFT and CET).

Alcohol Craving: Change in alcohol craving will be compared within-subjects between pre intervention and post intervention. In addition, differences in alcohol craving will be compared between groups (EFT and CET).

4.2 *Describe any primary or secondary safety endpoints. These should be included for all studies that are greater than minimal risk. (Minimal risk: The probability and magnitude of harm or discomfort anticipated in the research that are not greater in and of themselves than those ordinarily encountered in daily life or during the performance of routine physical or psychological examinations or tests.):*

This study's procedures are not more than minimal risk.

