Remote delivery of payments. To allow for payments that are both convenient and rapidly available, we will pay participants with reloadable prepaid cards through Greenphire ClinCard (www.greenphire.com), an FDIC-insured payment provider that specializes in clinical trial stipend payments that comply with IRB privacy regulations and considerations. At intake, each participant will receive a prepaid MasterCard debit card that can be used anywhere that accepts MasterCard. As payments are earned in the course of the study, additional funds will be added to the account for that participant. Funds are immediately available when added and participants can check their balance as desired. This system will allow frequent, immediately available payments without the burden of frequent laboratory visits that would negate some of the advantages of remote monitoring.

Daily alcohol use self-reports. Each day, participants will be asked to report how many alcoholic drinks they consumed the previous day (from the time they awoke to the time they fell asleep). We will ask them about the previous day's alcohol use instead of the

current day to best capture all drinks consumed each day without inconsistent response times complicating the measurement. Participants will be allowed to report this information at any time throughout the day, but will be encouraged through prompts to do so in the morning to increase the likelihood of accurate recall of previous day use. Participants will be allowed to report this information via the Remote Monitoring app. Participants may receive a reminder to report their previous-day drinking with text messages, followed by a phone call if they haven't contacted us appropriately. For completing this daily self-report, participants will receive \$1 in compensation.

Daily alcohol withdrawal symptoms. Each day, participants will be asked to report their alcohol withdrawal symptoms. Specifically, participants are instructed to report the maximum severity of alcohol withdrawal symptoms experienced "today" on a scale of 0 (no symptoms) to 9 (severe symptoms). Participants are instructed to contact the study team immediately if they have concerns about their withdrawal symptoms. Participants are provided with common alcohol withdrawal symptoms, including: anxiety, headache, insomnia, irritability; and severe symptoms including: convulsions and delirium tremors. Participants will be allowed to report this information via the Remote Monitoring app.

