16.0 Withdrawal of Subjects

16.1 Describe circumstances under which you anticipate subjects could be withdrawn from the research without their consent:

Participants may be withdrawn from the research without their consent if they become ineligible based on inclusion/exclusion criteria or learning of a contraindication for continuing, they demonstrate inconsistent delay discounting rates at the baseline session, there is an emergency, and/or they are not adherent with ARRC policies.

16.2 If applicable, describe any procedures for orderly termination (e.g., discontinuation of a study drug or debriefing after a behavioral intervention):

If a participant is withdrawn from the study, he or she will be informed that we have collected all the data required from their participation. If a participant is withdrawn or voluntarily discontinue, their compensation for the study will be pro-rated accordingly.

16.3 Describe procedures that you will follow when subjects withdraw from the research, including partial withdrawal from procedures with continued data collection (e.g., participant declines to continue with regular blood draws, but continues with periodic behavioral questionnaires):

If a participant is withdrawn or discontinued, they will be withdrawn from the entire study.

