Participants will be screened, using medical history and structured interviews, for a history of medical contraindications (e.g., recent myocardial infarction, current pregnancy), current unstable medical illness, and psychiatric disorders (including other substance use disorders). The studies will be conducted at FBRI. Participants will be free to withdraw from the study at any time, and their refusal to continue will not affect other medical care. In addition, if participants develop medical problems during the course of the study, assessments to determine whether participants should continue will be conducted by the Study Physician and necessary referrals will be provided. The risks enumerated above will be addressed by the following protections against risk, and reviewed by the Data and Safety Monitoring Board:

1. Adverse emotional reactions: [name] will monitor participants' adverse emotional reactions.
2. Alcohol withdrawal: In addition, participants who are not drinking alcohol may experience alcohol withdrawal symptoms during any of the laboratory sessions or if they are drinking less than they normally do during the proof-of-concept field study portion of this study. At each laboratory session, participants will complete the Alcohol Withdrawal Symptom Checklist (AWSC), a validated 17-item checklist of symptoms in which the

participant rates their experience from 0 (“Not at all”) to 4 (“Extreme”). A score of >23 on this checklist requires medical oversight for alcohol withdrawal and will trigger the research staff to contact [name]. [name] will speak with the participant to determine appropriateness and safety to continue in the study and to provide medical consultation and/or a referral to a clinic/primary care physician. If the participant produces a score of >23 on the checklist, [name] will be contacted to assess the participant’s risk and refer as necessary. We have successfully implemented these procedures with [name] in our previous and ongoing studies.

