The Alcohol Relative Reinforcement Schedule measures the extent to which alcohol serves as a reinforcer for an individual compared to other activities or substances⁴³. Participants will be asked to rate the frequency with which they engage in activities with and without alcohol and how enjoyable those activities are. Changes in alcohol reinforcing value before and after the intervention will be compared between groups (EFT and CET).

Alcohol Withdrawal Symptoms

The Alcohol Withdrawal Scale (AWSC⁴⁴) will be used to assess the severity of alcohol withdrawal symptoms. The AWS consists of a list of common withdrawal symptoms

associated with alcohol cessation, including physical and psychological manifestations. This is a 17-question where the withdrawal symptoms are scored by summing responses to a 5-point Likert scale. Severity of withdrawal symptoms will be compared between groups (EFT and CET).

Contemplation Ladder

The Contemplation Ladder is a 10-point scale that assesses readiness to change alcohol use. Changes in readiness to change alcohol before and after the intervention will be compared between groups (EFT and CET).

Penn Alcohol Craving Scale

The Penn Alcohol Craving Scale (PACS⁴⁵) is a 5-item questionnaire that measures an individual's craving to drink alcohol in the past week. Changes in alcohol craving before and after the intervention will be compared between groups (EFT and CET).

Statistical Principles

Data preparation and analysis occurs in 3 steps: (1) assessment of data integrity; (2) descriptive analyses; and (3) longitudinal analyses. To assess data integrity, the distribution of all variables will be examined, appropriate methods will be used for handling missing data, and distributional transformations will be applied if needed to meet normality assumptions. We will also evaluate data for, and report the results of, overall consistency (e.g., between self-reported use and breath sample results). A significance level of $p<0.05$ will be used for all analyses. Multiple testing corrections will be used to control for false positives. Here we present our current analysis plan for the proposed tests. We recognize that upon completion of data collection, we may identify additional hypotheses to test. We will first implement the analysis plan proposed herein, followed by additional hypotheses and analyses as secondary/explorative thereafter.

Statistical Analyses

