Objective 1: *We hypothesize that an intervention involving EFT will increase the temporal window and decrease alcohol valuation (consumption, demand, and craving).*

Our primary measure of alcohol use during the intervention period will be the daily self-reported number of drinks per day and the SOBERLINK breathalyzer screens. We will use generalized linear mixed models to compare the daily number of drinks between the EFT and CET groups. Mixed models is a method suited to the analysis of repeated measurement data. Here, the daily number of drinks will be modeled using a Poisson distribution. In the event the daily number of drinks exhibit over dispersion, other distributions, such as a negative binomial, will be considered. In a similar manner, dichotomous breathalyzer results data (positive or negative) throughout the 5-week field test will be analyzed as a function of intervention assignment, while accounting for time of day (morning, afternoon, evening) and repeated measures from each subject. Intrasubject correlation will be accounted for using an autoregressive correlation structure (AR(1)), since drinking days may be temporally related. In the event the AR(1) correlation structure is not representative of the data, other correlation structures will be considered. All missed assessments, although rare in our experience with similar field studies (approximately 5%), will be included as missing data. In the event of high rates of missing data, we will employ techniques consistent with the intention-to-treat paradigm, such as last observation carried forward methods or worst-case scenario (that all missing data is a positive BrAC measure).

Secondary analyses. In addition to the primary hypotheses listed above, we propose several additional analyses that will more fully characterize the behavior of our research participants and potentially lead to future research questions related to EFT in AUD. To this end, we hypothesize that EFT will result in changes (baseline versus post-intervention) in secondary outcome measures (e.g., Alcohol Withdrawal Symptoms Checklist). All these secondary hypotheses will be analyzed analogous to the primary hypothesis.

Covariate Plan:

We will test for individual differences in outcome measures for the intervention for each of these stratified variables. Therefore, we will include AUDIT score, SES, age, and gender in the analyses testing for an interaction between these variables and the intervention.

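### The SAP's only named contrast for alcohol withdrawal, baseline versus post-intervention on the summed checklist, could miss an EFT excess that resolves before Session 5; the daily severity scores and the protocol's own >23 event have no planned analysis

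*SAP*

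**What the plan says.** **Where the risk lies.** Protocol 17.2 (Protections Against Risk, item 2) says participants may have withdrawal symptoms at laboratory sessions or "if they are drinking less than they normally do during the proof-of-concept field study portion of this study".

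**What is collected.**
- The AWSC at every laboratory session (Protocol 17.2). A score above 23 "on this checklist requires medical oversight for alcohol withdrawal" and brings in the Study Physician.
- A daily item (Protocol 8.2), on which participants "report the maximum severity of alcohol withdrawal symptoms experienced" that day, from 0 to 9.

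**What is analysed.**
- SAP, Data Measures, on the summed AWSC: "Severity of withdrawal symptoms will be compared between groups (EFT and CET". No time point is given.
- SAP, Objective 1, Secondary analyses: "we hypothesize that EFT will result in changes (baseline versus post-intervention) in secondary outcome measures (e.g., Alcohol Withdrawal Symptoms Checklist". Then: "All these secondary hypotheses will be analyzed analogous to the primary hypothesis".
- The SAP mentions daily withdrawal reporting once, as a procedure of the baseline week, and never mentions the 23-point threshold.

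**Safety endpoints and review.** Protocol 4.2 sets no safety endpoint, on the ground that the study's "procedures are not more than minimal risk". Protocol 21.1 refers safety data review to an attached monitoring plan that is not among the documents.

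**The concern.** EFT is hypothesised to reduce drinking more than CET, so withdrawal is a harm that could plausibly differ by arm, and the protocol itself places it in the field weeks. The one contrast the SAP names looks at the end of those weeks. The measure that covers them day by day has no analysis, and neither does the event the protocol marks as clinically important.

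The documents present EFT as a possible therapeutic intervention. If the report says withdrawal severity did not differ, readers will take that as a safety finding, although it may rest on a visit made after any excess had passed.

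**Working it through.** **Group size.** The SAP's total of 52 completers reproduces. With f = 0.25, rho = 0.5, two measurements and alpha 0.01, the noncentrality is f² × N × 2/(1 − rho). At N = 52 this is 0.0625 × 52 × 2/0.5 = 13, with power 0.818; at N = 50 power is 0.799. That gives 26 per group. The protocol plans 38 per group. Both are used below.

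**Assumptions.** The documents give no AWSC standard deviation, episode rate or time course. The following are assumed: one episode per affected person, starting on a random day of days 1-28 and lasting L days; 24 points added to the AWSC while it lasts; SD 8; pre-post correlation 0.5; Session 5 on day 28; two-sided alpha 0.05; the AWSC reflecting the visit day only.

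**Share of episodes a visit can see.**
- Session 5 alone: L/28, or 7%, 11% and 18% for L = 2, 3 and 5.
- Sessions 4 and 5 together: 2L/28, or 14%, 21% and 36%.
- Episodes that start and end in week 1: none.

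**Baseline-to-Session-5 comparison, transient episodes.** The SD of change is 8 × √(2 × (1 − 0.5)) = 8. The expected difference is (EFT rate − CET rate) × L/28 × 24. For 30% versus 5%:
- L = 2: 0.25 × 2/28 × 24 = 0.43 points
- L = 3: 0.25 × 3/28 × 24 = 0.64 points
- L = 5: 0.25 × 5/28 × 24 = 1.07 points

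The standard error with 38 per group is 8 × √(2/38) = 1.84 points, so each difference is well under one standard error. By simulation, a t-test on the change rejects in about 5-8% of trials across 20% or 30% versus 5%, L = 2 to 5, and 26 or 38 per group.

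**Same comparison, excess still present at Session 5.** Take 26 per group and a correlation of about 0.4 between the two visits. The SD of change is √(2 × 0.6) = 1.095 SD units, and power ≈ Φ(δ/1.095 × √13 − 1.96). This gives 0.38, 0.75 and 0.91 for δ = 0.5, 0.8 and 1.0 SD.

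**What daily scores could add.** A second simulation used 26 per group, a between-person share of variance of 0.4, day-to-day AR(1) of 0.4, complete reports, and an excess of 0.5-1.0 SD that ends before Session 5. Detection rates were:

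| Length of excess | Baseline-to-Session-5 change | 28-day daily mean, less baseline week |
|---|---|---|
| 7 days | about 5% | 16-48% |
| 14 days | 4-6% | 50-97% |
| 28 days | about 5% | 96-100% |

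The week-1 mean alone detected it in 88-100% of trials, which is the reason to model by week.

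**The >23 event.** With 38 per group and 30% versus 5%, counting it only at Sessions 4 and 5 gives Fisher power of 0.4-13% for L = 2 to 5. With 0 of 26 events, the one-sided 95% upper limit is 1 − 0.05^(1/26) = 10.9%. These counts are worth reporting but cannot carry a test.

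**The case against.** **Session 4 may already be in the model.** The primary method is a repeated-measures mixed model, secondary outcomes are to follow it, and the AWSC is taken at Session 4. This reading is open. The SAP does not state it, though, and the sentence just before names baseline versus post-intervention. Even with Session 4 included, the two visits see 14-36% of episodes under the assumptions above, and the daily score stays unused. The t-test used in the working stands in for the named contrast; it is not the SAP's specified model.

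**The AWSC may look back over several days.** The documents give no recall period. With an assumed 7-day recall, Sessions 4 and 5 together would see 2(L + 6)/28, or 57-79%, and the 5-8% rejection rate would rise. This weakens the size of the problem, not its direction.

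**Safety is handled elsewhere.** Individuals above 23 are referred to the Study Physician, the listed risks go to a Data and Safety Monitoring Board, and the attached plan may include a review by arm. The gap can be asserted for the protocol and SAP only. A staff trigger is still not a result by arm.

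**Severe cases do not simply vanish.** A reader might infer from Protocol 16.3 ("If a participant is withdrawn or discontinued, they will be withdrawn from the entire study") that the worst cases drop out of the comparison unseen. The documents do not establish that. A high Session 4 score is recorded, the SAP compares attrition by arm between Sessions 3 and 4 and between 4 and 5, and Protocol 8.2 says post-intervention data are collected however many intervention days were completed. Sections 8.2 and 16.3 do not fit together for people taken out of the study.

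**Power from counting episodes on the daily score.** A Fisher test on any episode would have 79% power (38 per group, 30% versus 5%) only if the daily score identified every episode without error. No cut-off on 0-9 is defined. Background reporting of 10-30% in both arms lowers the figure to 53-26%. It is not relied on here.

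**Conclusion.** The concern holds in a limited form. The daily 0-9 score and the >23 event have no planned analysis in either document, and the one contrast named for withdrawal is poorly placed to show an excess confined to the field weeks. Such an excess could be missed: rejection is about 5-8% for assumed 2- to 5-day episodes, and 4-6% for an assumed 0.5-1.0 SD excess that ends before Session 5.

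A reader might infer that any EFT excess would be reported as no difference. The documents do not support that. An excess lasting to Session 5 has power of about 0.38-0.91 for 0.5-1.0 SD, and Session 4 may enter the model. Nor do they show that EFT raises withdrawal, or that it goes unmonitored. All withdrawal rates, durations and standard deviations here are assumptions.

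**What to change.** Add the following to the SAP, for all randomised participants and using data already collected:

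1. Compare daily 0-9 severity between arms over the intervention days on which it was collected. Use a mixed model with group by week, or an ordinal model of each participant's maximum, adjusted for the baseline week. Show the days reported by arm.
2. Report by arm, with exact confidence intervals and no claim of power, the number with AWSC above the protocol's existing threshold at any post-randomisation session, and the number taken out of the study or referred because of withdrawal symptoms.
3. State that the Session 4 AWSC enters the repeated-measures model. Do not use the baseline-to-post contrast alone to conclude that EFT does not increase withdrawal.
4. Reconcile two sets of passages. Protocol 8.2 asks for the daily score each day, but its description of Monitoring Part 2, unlike those of the baseline week and Part 1, does not mention it. Protocol 8.2 and 16.3 differ on post-intervention data for people taken out of the study.

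The cost is SAP wording, one table and one model, with no new visits or participants. Intervals will be wide, and the safety statement may be less reassuring.

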Height: Self report height

Penn Alcohol Craving Scale: Assesses alcohol craving.

Reward Responsiveness Scale: Measures responsiveness to reward through a single component measure

Timeline FollowBack Interview (TLFB): Assesses the number of alcoholic drinks and other substances daily for the past 30 days, or since the previous assessment, whichever is fewer.

Urinalysis: Assesses substance use and/or pregnancy.

Weight: Self report weight

**8.4 What data will you collect during the study and how you will obtain them?
Please include descriptions of electronic data collection, database matching, and app-based data collection:**

All of the survey and questionnaire data will be collected using Qualtrics, online survey platforms used to develop, administer, and collect participant data in a secure password protected database. Only study personnel will have access to the survey and collected data.

The fMRI tasks will be administered using python-coded tasks, wherein the participant data will be securely collected on a password protected shared-drive hosted by FBRI.

fMRI analyses. GLM-based analysis will be performed using AFNI. We will perform slice timing correction, motion correction, and spatial smoothing (Gaussian kernel with full-width-at-half-maximum of 2.0 Å~ the voxel size). Linear regression coefficients (beta-weights) and t-statistic maps will be calculated. Since fMRI relies on neurovascular coupling, which changes due to the vasoactive properties of alcohol, nicotine, and caffeine (short term) and for vascular damage (long term for AUD individuals), we will model our data with a finite impulse response basis set rather than a “standard” HRF model.

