We will use a 3T Siemens MAGNETOM Prisma^{fit} scanner (Siemens, Erlangen, Germany) with a 20-channel head/neck coil. T1-weighted images will be acquired at $1 \times 1 \times 1 \text{ mm}^3$ resolution using 3D MPRAGE, FOV = $256 \times 256 \times 176 \text{ mm}^3$, TR/TE/TI = 1950/4.44/950 ms, FA = 12° , phase partial Fourier 7/8, slice partial Fourier 6/8, GRAPPA factor = 4 with 33 reference lines, and bandwidth = 140 Hz/pixel. Functional BOLD data will be acquired using EPI with thirty-three 4 mm interleaved slices with a 10% slice gap, TR/TE = 2000/30 ms, FA = 10° , in-plane resolution of $3.4 \times 3.4 \text{ mm}^2$, anterior-to-posterior phase encoding and a bandwidth = 2442 Hz/pixel. Participants will be instructed to keep their eyes open during the scan and direct their gaze on a white plus (+) sign centered on a black background.

Alcohol Consumption

Changes in drinks per day and the number of positive breath alcohol samples (BrAC) will be compared within subjects between pre-intervention and post-intervention. In

addition, differences in drinks per day and the number of positive BrAC samples will be compared between groups (EFT and CET). A Timeline Follow Back (TLFB⁴⁰) will be conducted during Session 2 (pre-intervention) and Session 6 (1-month follow-up) to assess the number of alcoholic drinks consumed daily for the past 30 days. During the intervention period (from Session 2 to Session 5), participants will report daily the number of alcoholic drinks consumed.

Alcohol Urges Questionnaire (AUQ)

The Alcohol Urges Questionnaire ⁴¹ will be used to assess craving for alcohol. This 8-question measure of drinking urges is scored by summing responses to a 7-point Likert scale. The dependent measure of the summed score will be compared within subjects between pre-intervention and post-intervention. In addition, differences in alcohol craving will be compared between groups (EFT and CET).

Alcohol Use Disorders Identification Test (AUDIT)

The Alcohol Use Disorders Identification Test (AUDIT⁴²) will be used to assess hazardous or harmful alcohol use. AUDIT is a 10-item screening tool that assesses alcohol consumption, drinking behaviors, and alcohol-related problems. Differences in alcohol AUDIT scores will be compared between groups (EFT and CET).

Alcohol Relative Reinforcement Schedule (ARRS)

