Sensitivity Analyses:

Due to the longitudinal nature of the experimental design, some participant drop-out is expected. We will perform sensitivity analyses to identify and document any potential biases that may arise due to participant drop out.

- Attrition prior to randomization: We will evaluate if any demographics and assessment values from S1 are associated with participant drop-out at S2.
- Attrition between Session 3 and Session 4: We will evaluate if differences in the attrition rates between EFT and CET exist during the first 2-week field test. Moreover, we will evaluate if demographics and assessment values are associated with participant drop-out prior to S4.
- Attrition between Session 4 and Session 5: We will evaluate if differences in the attrition rates between EFT and CET exist during the second 2-week field test. Moreover, we will evaluate if demographics and assessment values are associated with participant drop-out prior to S5.
- Missing daily reports/BrAC during 4-week intervention: We will evaluate if there is an association between the percentage of missing data points during the 4-week intervention and average daily drinks to assess if missing data is missing at random. For example, a negative correlation between the average daily drinks and percentage missing data may suggest missing daily values are not random. In addition, we will evaluate if missing BrAC values are associated with time of day.
- Attrition at 1-month follow-up: We will evaluate if there are differences in the 1-month follow-up rates between the EFT and CET groups. We will evaluate if average daily consumption is associated with 1-month follow-up rates. We will evaluate if participant demographics and assessment values are associated with 1-month follow-up rates.

We will report the results of all germane sensitivity analyses in all publications and discuss potential biases that may result from participant drop-out.

Exploratory Analyses:

In addition, we will perform an exploratory mediation analysis evaluating if AUDIT score, SES, age, gender, psychiatric comorbidities, executive function, family history, impulsivity, and reward sensitivity mediate the relationship between intervention and the primary outcomes. This analysis will be completed using bootstrap-based approaches, as described in Preacher and Hayes.

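### The SAP's check on missing daily reports cannot show that they are missing at random, and it barely registers participants who skip their own heavy-drinking days

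*SAP*

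**What the plan says.** For drinking, the SAP (Statistical Analyses, Objective 1) states: "We will use generalized linear mixed models to compare the daily number of drinks between the EFT and CET groups". On gaps in the daily data it says: "All missed assessments, although rare in our experience with similar field studies (approximately 5%), will be included as missing data". If missing data are frequent, it names as examples "last observation carried forward methods or worst-case scenario (that all missing data is a positive BrAC measure"). It does not say what rate counts as frequent.

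The SAP's Sensitivity Analyses then relate the percentage of data points missing over the four intervention weeks to "average daily drinks to assess if missing data is missing at random". The example given is that "a negative correlation between the average daily drinks and percentage missing data may suggest missing daily values are not random". The same bullet looks at missing breath samples by time of day. It does not mention arm, whereas the bullets on attrition after randomization do compare EFT with CET.

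Two other passages bear on this. Statistical Principles promises a check of "overall consistency (e.g., between self-reported use and breath sample results"). On the Timeline Followback (TLFB), Protocol 8.3 gives its look-back as "Assesses the number of alcoholic drinks and other substances daily for the past 30 days, or since the previous assessment, whichever is fewer", while the SAP (Alcohol Consumption) says it "will be conducted during Session 2 (pre-intervention) and Session 6 (1-month follow-up) to assess the number of alcoholic drinks consumed daily".

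**The concern.** The mixed model leaves missed days as missing, so it is valid only if, given what was recorded, missingness does not depend on the unrecorded count. The correlation cannot tell whether that holds. If missingness depends only on recorded drinking, a correlation can appear although the data are missing at random. If people omit days because those days were heavy, the data are not missing at random, yet the correlation can be zero.

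The check uses one number per person, the mean of recorded days, and compares people. Someone who leaves out their own heavy days lowers that mean only slightly relative to the spread between people. If heavier drinkers also miss more days, the correlation becomes positive, the opposite sign to the SAP's example.

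What biases EFT versus CET is a difference in skipping between arms, which the bullet does not examine. EFT participants who leave out heavy days would appear to drink less, and nothing in the sensitivity list would show how far the estimate moves.

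**Working it through.** **Inputs from the documents.** 28 intervention days (Protocol 5.2); about 5% missed assessments and a count model (SAP, Objective 1); significance level 0.05 (SAP, Statistical Principles); 26 completers per arm (SAP, Sample size). The completer number reproduces: f = 0.25, correlation 0.5, two measurements, noncentrality 0.25² × 52 × 2 / (1 − 0.5) = 13.0. With alpha 0.01 and a noncentral F on 1 and 50 degrees of freedom, power is 0.818 at N = 52 (0.799 at N = 50). The plan gives no figure for bias from missing days.

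**Step 1: size of the bias.** Let m be the share of EFT days missing and r the mean drinks on those days divided by the overall mean. With CET missing at random and no true effect,

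observed / true EFT mean = (1 − m·r) / (1 − m).

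The values of r are assumed.

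| m | r = 1.5 | r = 2 | r = 2.5 |
|---|---|---|---|
| 5% | 0.925/0.95: 2.6% too low | 0.90/0.95: 5.3% | 0.875/0.95: 7.9% |
| 10% | 0.85/0.90: 5.6% | 0.80/0.90: 11.1% | 0.75/0.90: 16.7% |

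**Step 2: does the correlation notice?** Simulation with no true effect, 1,500 trials per setting, 26 or 38 per arm, 28 days. Assumed: mean 5 drinks/day (the SAP's retention text expects more than 4 per drinking day), between-person coefficient of variation 0.5, negative binomial dispersion 0.3 to 0.6. An own-heavy day is one above the person's own 75th percentile. The test is Pearson's r pooled over arms, two-sided 0.05. Bias is the ratio of arm means, not a refitted mixed model.

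| Pattern | False benefit | Mean r | Significantly negative |
|---|---|---|---|
| EFT skips 20% of own-heavy days (about 4% missing); CET 5% at random | 4.8-6.3% | about 0 | 2-3% |
| EFT skips 50% of own-heavy days (about 11%); CET 11% at random | 12.7-16.7% | −0.02 to 0.01 | 1.5-3.4% |
| As above, CET 5% at random | 12.7-16.6% | about −0.1 | 7-16% |
| 50% on average, varying between people; CET 11% at random | 13.2-17.4% | about −0.1 | 6-14% |
| EFT skips 50% of days with 8 or more drinks; CET 11% at random | 12.2-16.4% | +0.37 to +0.44 | 0% (positive: 76-96%) |
| Both arms skip 50% of days with 8 or more drinks | 0% | about +0.7 | 0% (positive: 100%) |

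In the second row a negative flag appears at about the 2.5% expected by chance. The reason is scale: a 12.7-16.7% fall in a mean of 5 is 0.64-0.84 drinks, against a between-person SD of 0.5 × 5 = 2.5.

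**Step 3: smoother skipping.** Here the log-odds of missing a day rise by 1.5 per log-drink within a person, in EFT only (dispersion 0.4, 26 per arm). The false benefit is about 4% at 5% missing and 8-9% at 12%. Mean r is between −0.02 and 0, with a negative flag in 2.5-3.6% of trials. A paired within-person comparison of drinks on missed versus reported days, assuming an accurate second stream, detects the pattern in 76% of trials at 5% missing and 98% at 12%.

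**The case against.** The SAP sets out to look for an association; the negative sign is only an example, and hedged. It has no pass rule, and it commits to reporting the sensitivity analyses and discussing possible bias. Read two-sidedly, the check does see some patterns. With the fixed eight-drink threshold in EFT it flags 76-96% of trials. With heavier drinkers also missing more (smoother model, 12% missing), it flags 84% to over 99%. A reader might infer that the check can detect nothing; that goes too far. The weakness is specific to within-person skipping.

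A reader might also infer that the plan would let through a false benefit of around 12%. No such figure is in the documents. Solving Step 1 for 12% gives r = (1 − 0.88 × 0.95)/0.05 = 3.28 at the SAP's 5% missing, and (1 − 0.88 × 0.90)/0.10 = 2.08 at 10%. It therefore takes about twice the expected missingness, concentrated on heavy days, in EFT alone.

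There are safeguards. Breath samples are paid whatever the result, complete days earn a bonus, and late drink reports prompt reminders and a call (Protocol 8.2 and 15.4). Participants had to report on 5 of 7 baseline days to continue. The SAP also plans the consistency check and a fallback for frequent missing data. These lower the risk but do not test for skipping. The consistency check is not described as addressing why days are missing. The fallback has no trigger level, its worst case covers breath samples only, and carrying the last value forward would replace a skipped heavy day with an earlier one.

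Finally, a reader might infer that the SAP discards TLFB interviews covering the intervention. Protocol 8.3 gives a look-back window but no list of sessions, and neither document schedules TLFB at Sessions 3 to 5.

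**Conclusion.** The concern holds in this form: the person-level correlation cannot separate missing at random from missing not at random, and it has almost no ability to detect people skipping their own heavy days. It is not specified by arm, and no analysis in that list re-estimates the effect.

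The possible false EFT benefit is about 3-8% at the expected 5% missing and about 6-17% at 10-12%. These ranges assume that skipping of heavy days is confined to EFT and that CET days are missing at random; the drink distribution and skipping rates are also assumed. Equal skipping in both arms leaves the rate ratio unbiased. Nothing in the documents says that such skipping will occur. The point is that the stated check could not rule it out, and the trial already collects data that would examine it better.

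**What to change.** 1. Delete the statement that this correlation assesses missing at random. It can stay as a description, read two-sidedly and shown by arm.
2. Compare daily missingness between EFT and CET. Fit two logistic mixed models with a participant effect: a missed breath sample given the drinks reported for that day, and a missed drink report given that day's BrAC. Separate each person's own mean from the daily deviation, and include arm and arm-by-drinking terms. Drink reports refer to the previous day, so align the streams by the day described.
3. Re-estimate the EFT-CET rate ratio by multiple imputation of daily counts with BrAC as auxiliary. Add a delta-adjusted version that multiplies the imputed counts, by arm, over a grid fixed in advance, and report where the conclusion changes.
4. Reconcile the TLFB look-back in Protocol 8.3 with Sessions 2 and 6 in the SAP. A 30-day recall one month after the intervention would largely miss the 28 intervention days. Use TLFB day values here only if they are collected for those days; adding interviews would be new data collection.

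Items 1 to 3 cost SAP wording and some analysis. Their limit is that both streams come through the same app and may go missing together. The within-person detection rates above are therefore best cases, and days with neither stream rest on the delta adjustment.
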